11. STUDY CALENDAR

Schedules shown in the Study Calendar below are provided as an example and should be modified as appropriate.

Baseline evaluations are to be conducted within 3 weeks prior to start of protocol therapy. Scans and x-rays must be done \leq 4 weeks prior to the start of therapy. In the event that the patient's condition is deteriorating, laboratory evaluations should be repeated within 48 hours prior to initiation of the next cycle of therapy.

All protocol visits have a plus or minus 3 business day window.

Rituxan should be given after ipi/nivo infusion for subjects on Arm B. The timing of Rituxan is 1-2 days (preferably 1 day) following ipi-nivo infusion.

		1	ı	ı						1	1					
	Pre- Study	Wk 1	Wk 2	Wk 3	Wk 4	Wk 5	Wk	Wk	Wk 8	Wk 9	Wk 10	WK 12	Wk 13	WK 17	WK 21	Off Study
IPI 3mg/kg + Nivo 1mg/kg		X			X			X			X					
Nivo 480mg IV ^a													X	X	X	
Rituxan IV (loading dose)			X													
Rituxan SQ				X	X	X										
Informed consent	X															
Demographics	X															
Medical history	X															
Con Medications	X	X	X	X	X			X			X		X	X	X	X
Physical exam	X	X			X			X			X		X	X	X	X
Vital signs	X	X	X	X	X			X			X		X	X	X	X
Height	X															
Weight	X	X	X	X	X			X			X		X	X	X	X
Performance status	X	X			X			X			X		X			X
CBC w/diff, plts	X	X	X	X	X			X			X		X	X	X	X
Serum chemistry with LDH	X	X	X	X	X			X			X		X	X	X	X
EKG (12-lead)	X															
Adverse Event	X	X	X	X	X			X			X		X	X	X	X
Radiologic Evaluation ^b	X											X				
B-HCG	X															
Hepatitis B (HepB surface antigen and HepB core antibody), Hep C and HIV serology	X															
TSH, Free T, ACTH, cortisol	X				X			X			X		X	X	X	X
Blood correlative	X		X		X						X		X			X
Fresh Tissue Biopsy ^c	X				X											

^a given every 4 weeks starting at Week 13 for up to 13 doses.

^b CT scans n/c/a/p with contrast every 12 weeks for the first two years, then every 6 months for five years. MRI brain with contrast should be done at baseline, then every 6 months for patients with no history of CNS mets as per standard of care; every 3 months for those with a history of CNS metastases for two years, then every 6 months. CT head can be used for patients with a contraindication to MRI.

^C Tissue biopsy before week 4 is optional but encouraged whenever possible.

12. MEASUREMENT OF EFFECT

12.1 Antitumor Effect

For the purposes of this study, patients should be re-evaluated for response every 12_weeks. Please see study calendar for details on scan requirements.

Response and progression will be evaluated in this study using the new international criteria proposed by the revised Response Evaluation Criteria in Solid Tumors (RECIST) guideline (version 1.1) [Eur J Ca 45:228-247, 2009]. Changes in the largest diameter (unidimensional measurement) of the tumor lesions and the shortest diameter in the case of malignant lymph nodes are used in the RECIST criteria.

12.1.1 Definitions

Evaluable for toxicity. All patients will be evaluable for toxicity from the time of their first treatment with ipilimumab/nivolumab.

Evaluable for objective response. Only those patients who have measurable disease present at baseline, have received at least one cycle of therapy, and have had their disease re-evaluated will be considered evaluable for response. These patients will have their response classified according to the definitions stated below. (Note: Patients who exhibit objective disease progression prior to the end of cycle 1 will also be considered evaluable.)

Evaluable Non-Target Disease Response. Patients who have lesions present at baseline that are evaluable but do not meet the definitions of measurable disease, have received at least one cycle of therapy, and have had their disease re-evaluated will be considered evaluable for non-target disease. The response assessment is based on the presence, absence, or unequivocal progression of the lesions.

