1.2 Secondary Objectives

- To evaluate the safety and tolerability (in terms of Rituxan-related adverse events) in patients with melanoma receiving CCB.
- To compare objective response rate in patients receiving CCB therapy + Rituxan versus CCB therapy alone.
- To compare 1 year overall and progression-free survival in patients receiving CCB therapy + Rituxan versus CCB therapy alone.
- To compare changes in CD21^{lo} B cells in patients receiving CCB therapy + Rituxan versus CCB therapy alone.
- To compare changes in T cells in patients receiving CCB therapy + Rituxan versus CCB therapy alone.

Exploratory Objectives

• To compare treatment induced changes in tumor tissue in patients receiving CCB therapy + Rituxan versus CCB therapy alone.

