5.3 Duration of Follow Up

Patients will be followed for 4 weeks after removal from study or until death, whichever occurs first. Patients removed from study for unacceptable adverse event(s) will be followed until resolution or stabilization of the adverse event.

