12.1.4.3 Evaluation of Best Overall Response

The best overall response is the best response recorded from the start of the treatment until disease progression/recurrence (taking as reference for progressive disease the smallest measurements recorded since the treatment started). The patient's best response assignment will depend on the achievement of both measurement and confirmation criteria.

For Patients with Measurable Disease (i.e., Target Disease)

Target	Non-Target	New	Overall	Best Overall Response when
Lesions	Lesions	Lesions	Response	Confirmation is Required*
CR	CR	No	CR	≥4 wks. Confirmation**
CR	Non-CR/Non-	No	PR	
	PD			1 xxlxa Confirmation**
CR	Not evaluated	No	PR	≥4 wks. Confirmation**
PR	Non-CR/Non-	No	PR	

	PD/not evaluated			
SD	Non-CR/Non- PD/not evaluated	No	SD	Documented at least once ≥4 wks. from baseline**
PD	Any	Yes or No	PD	
Any	PD***	Yes or No	PD	no prior SD, PR or CR
Any	Any	Yes	PD	

^{*} See RECIST 1.1 manuscript for further details on what is evidence of a new lesion.

Note: Patients with a global deterioration of health status requiring discontinuation of treatment without objective evidence of disease progression at that time should be reported as "symptomatic deterioration." Every effort should be made to document the objective progression even after discontinuation of treatment.

For Patients with Non-Measurable Disease (i.e., Non-Target Disease)

Non-Target Lesions	New Lesions	Overall Response
CR	No	CR
Non-CR/non-PD	No	Non-CR/non-PD*
Not all evaluated	No	not evaluated
Unequivocal PD	Yes or No	PD
Any	Yes	PD

^{* &#}x27;Non-CR/non-PD' is preferred over 'stable disease' for non-target disease since SD is increasingly used as an endpoint for assessment of efficacy in some trials so to assign this category when no lesions can be measured is not advised

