14. STATISTICAL CONSIDERATIONS

14.1 Study Design/Endpoints

Endpoints:

Primary:

• Primary endpoint is the rate of CTC (v5.0) grade 3 or greater immune-related adverse events at 6 months of follow up.

Secondary:

- Rate of CTC (v5.0) toxicity related to Rituxan.
- Objective tumor response as assessed by RECIST v1.1 and irRECIST at 12 weeks and every 12 weeks thereafter.
- Rates of overall and progression-free survival at 1 year following initiation of therapy.

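### The only response-evaluable set the plan defines drops randomised patients with no tumour re-evaluation, so the between-arm ORR comparison would rest on a group selected after randomisation

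*Combined protocol and SAP*

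**What the plan says.** Section 1.2 lists as a secondary objective "To compare objective response rate in patients receiving CCB therapy + Rituxan versus CCB therapy alone". Section 14.1 gives the endpoint: "Objective tumor response as assessed by RECIST v1.1 and irRECIST at 12 weeks and every 12 weeks thereafter".

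The set comes from section 12.1.1, which is worded as a restriction. Only patients with measurable disease at baseline who "have received at least one cycle of therapy, and have had their disease re-evaluated will be considered evaluable for response" qualify. A note adds: "Patients who exhibit objective disease progression prior to the end of cycle 1 will also be considered evaluable". The non-target set in the same section also requires re-evaluation, so it does not recover anyone left out of the first.

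Section 14 names no other ORR set and gives no rule for a missing response. Section 14.2 has two ORR stopping rules. One stops for fewer than 2 responders among the first 12 patients treated with Rituxan. The other calculates ORR after every 10 patients enrolled and stops if the arms differ by more than 30%; it does not say which patients form the denominator.

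Other text bears on how often a patient might go unassessed. The study calendar asks for "CT scans n/c/a/p with contrast every 12 weeks for the first two years", starting at week 12. Section 12.1.4.3 says "Every effort should be made to document the objective progression even after discontinuation of treatment". Section 5.3 says "Patients will be followed for 4 weeks after removal from study or until death, whichever occurs first", but also "Patients removed from study for unacceptable adverse event(s) will be followed until resolution or stabilization of the adverse event".

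**The concern.** Whether disease was re-evaluated is known only after randomisation and can depend on treatment, through death, withdrawal, toxicity or clinical decline. Conditioning on it gives up the protection of randomisation for this comparison. The patients lost this way are unlikely to be typical, and leaving them out raises the reported rate relative to counting them as non-responders. If the arms lose different numbers, the arm difference moves as well.

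Section 2.4 says that preventing immune toxicity is worthwhile only if anti-tumour immunity is preserved. The ORR comparison is one of the plan's checks on that, alongside PFS and OS at 1 year, and ORR also drives early stopping. In an open-label trial, the denominator should be settled before arm results are seen.

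**Working it through.** **The plan's own ORR figure.** Section 14.2 gives about 92% for at least 2 responders among 12 at a 30% response rate. With X ~ Bin(12, 0.30), P(X ≥ 2) = 0.915, which agrees. This rule counts treated patients and does not settle the between-arm denominator.

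**Inputs.** From section 14.2: 22 per arm, ORR about 42%, threshold above 30%. Assumed, because the documents give no figure: the numbers unassessed, and that all 22 per arm have measurable disease unless stated. Nine responders of 22 (40.9%) is the count nearest 42%.

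**One arm.** Evaluable-only ORR = 9/(22 − m), with m unassessed:

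| m | 0 | 1 | 2 | 3 | 4 |
|---|---|---|---|---|---|
| ORR | 40.9% | 42.9% | 45.0% | 47.4% | 50.0% |

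With the unassessed counted as non-responders, ORR stays at 9/22 = 40.9% throughout.

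**Arm difference.** With 9/22 in each arm and 1 versus 4 unassessed, 9/18 − 9/21 = 50.0 − 42.9 = 7.1 points, from the denominator alone. With 20 measurable per arm and 8 responders, 8/16 − 8/19 = 7.9 points. With 18 and 7 responders, 7/14 − 7/17 = 8.8 points. For scale, the Wald 95% half-width at 9/22 each is 1.96 × √(2 × 0.409 × 0.591 / 22) = 29.1 points.

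**The 30% rule.** Assume one unassessed per arm, true ORR 42% in both arms, and responders among the assessed ~ Bin(n − 1, 0.42) independently. The rule trips at the smallest responder gap d with d/(n − 1) > 0.30 (evaluable) or d/n > 0.30 (all patients). Each row is that look alone, not cumulative.

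| Per arm (n) | Trips at, evaluable | Trips at, all | Chance, evaluable | Chance, all |
|---|---|---|---|---|
| 5 | 2 | 2 | 28.2% | 28.2% |
| 10 | 3 (3/9 = 33.3%) | 4 (3/10 = 30.0%, not above) | 23.1% | 9.2% |
| 15 | 5 | 5 | 8.3% | 8.3% |
| 20 | 6 (6/19 = 31.6%) | 7 (6/20 = 30.0%, not above) | 6.9% | 3.1% |
| 22 | 7 | 7 | 4.1% | 4.1% |

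The denominator matters only where it moves the integer threshold. With two unassessed per arm, thresholds also part at 5 per arm (1/3 = 33.3% trips; 1/5 = 20.0% does not) and at 15 (4/13 = 30.8% trips; 4/15 = 26.7% does not), but still not at 22 (6/20 = 30.0% and 6/22 = 27.3%; neither trips).

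Unequal loss can also work the other way. Take 5 per arm, 3 responders in Arm A, and 1 responder with 2 unassessed in Arm B. Over all patients the gap is 3/5 − 1/5 = 40.0 points (stop); over evaluable patients it is 3/5 − 1/3 = 26.7 points (continue).

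**The case against.** **Loss may be rare.** The scan footnote is not tied to staying on treatment, and effort to document progression after stopping is asked for. Section 6 keeps patients who stop Rituxan for toxicity in their arm for follow-up. All of this stands as limiting the problem. None of it says how an unassessed patient counts: the intent-to-treat wording in section 6 concerns follow-up, not an ORR denominator. A reader might infer from the 4-week follow-up in section 5.3 that such losses will occur. The text shows only that they can. A patient removed in week 5 could finish follow-up by week 9, before the first scan; those removed for adverse events are followed longer, though no scan is required.

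**The plan might be called silent.** A reader might infer that nothing says how these patients count. Section 12.1.1 does say: it excludes them. The weakness is the stated rule, together with the absence of any other denominator in section 14. The note on early progression does not rescue them. Objective progression itself has to be assessed, so the note most naturally relaxes the one-cycle requirement. Nor does the section say whether an unscheduled scan or a caliper reading would be enough re-evaluation.

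**Section 14.2 might imply an all-patient denominator.** Its count of patients enrolled sets when ORR is calculated, and its count of the first 12 treated belongs to a one-arm rule. Read as the between-arm denominator, either would conflict with the restriction in 12.1.1.

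**Counting missing as non-response is not neutral.** This stands. The design expects more grade 3 or greater immune events in control (60% versus 20%). If toxicity leads to missed scans, the convention would lower control ORR and could hide harm from Rituxan. It needs supportive analyses beside it.

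**Conclusion.** The concern holds as a modest one, to consider rather than to insist on. Followed as written, the plan gives an ORR in patients selected by a post-randomisation event. Relative to the non-responder convention that rate is too high, and the arm difference can be biased in either direction if loss is unequal.

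The sizes rest entirely on assumed loss. One versus four unassessed shifts the arm difference by 7.1 points (up to 8.8 in the cases with fewer measurable patients), small against sampling error of about 29 points. For the stopping rule, a reader might take the 10-per-arm result, 23.1% versus 9.2%, as typical. It is the largest gap among the looks tabulated; with one unassessed per arm the denominator makes no difference at 5, 15 or 22. The supported statement is that the rule's behaviour depends on an unstated denominator at some looks. The primary endpoint, PFS and OS do not use this set.

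**What to change.** In sections 12.1.1 and 14.2:

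- Base the between-arm ORR comparison on all randomised patients with measurable disease at baseline. Count those with no post-baseline assessment as non-responders, stated as a convention because their response is unknown.
- Report the number unassessed, with reasons, by arm.
- Keep the evaluable-only ORR as supportive, and show the range of the arm difference with unassessed patients counted as responders or as non-responders.
- State that the 30% between-arm rule uses the same denominator.

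The cost is a few sentences and no new data collection. Reported ORR will read somewhat lower, and any true responder who was never assessed counts as a failure. The masking risk can be sized. Take 9/22 observed in each arm, with 1 Rituxan and 4 control patients unassessed. The convention gives a difference of 0, and the evaluable-only Rituxan-minus-control difference is 42.9 − 50.0 = −7.1 points. The bounds run from 9/22 − 13/22 = −18.2 to 10/22 − 9/22 = +4.5 points. The supportive rate and the range should therefore be reported alongside the main figure.

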12.1.2 Disease Parameters

Measurable disease. Measurable lesions are defined as those that can be accurately measured in at least one dimension (longest diameter to be recorded) as \geq 20 mm by chest x-ray or as \geq 10 mm with CT scan, MRI, or calipers by clinical exam. All tumor measurements must be recorded in millimeters (or decimal fractions of centimeters).

Note: Tumor lesions that are situated in a previously irradiated area might or might not be considered measurable. *If the investigator thinks it appropriate to include them, the conditions under which such lesions should be considered must be defined in the protocol.*

Malignant lymph nodes. To be considered pathologically enlarged and measurable, a

Version Date: 04-05-2021 v6.0

lymph node must be \geq 15 mm in short axis when assessed by CT scan (CT scan slice thickness recommended to be no greater than 5 mm). At baseline and in follow-up, only the short axis will be measured and followed.

Non-measurable disease. All other lesions (or sites of disease), including small lesions (longest diameter <10 mm or pathological lymph nodes with ≥10 to <15 mm short axis), are considered non-measurable disease. Bone lesions, leptomeningeal disease, ascites, pleural/pericardial effusions, lymphangitis cutis/pulmonitis, inflammatory breast disease, and abdominal masses (not followed by CT or MRI), are considered as non-measurable.

Note: Cystic lesions that meet the criteria for radiographically defined simple cysts should not be considered as malignant lesions (neither measurable nor non-measurable) since they are, by definition, simple cysts.

'Cystic lesions' thought to represent cystic metastases can be considered as measurable lesions, if they meet the definition of measurability described above. However, if non-cystic lesions are present in the same patient, these are preferred for selection as target lesions.

Target lesions. All measurable lesions up to a maximum of 2 lesions per organ and 5 lesions in total, representative of all involved organs, should be identified as **target lesions** and recorded and measured at baseline. Target lesions should be selected on the basis of their size (lesions with the longest diameter), be representative of all involved organs, but in addition should be those that lend themselves to reproducible repeated measurements. It may be the case that, on occasion, the largest lesion does not lend itself to reproducible measurement in which circumstance the next largest lesion which can be measured reproducibly should be selected. A sum of the diameters (longest for non-nodal lesions, short axis for nodal lesions) for all target lesions will be calculated and reported as the baseline sum diameters. If lymph nodes are to be included in the sum, then only the short axis is added into the sum. The baseline sum diameters will be used as reference to further characterize any objective tumor regression in the measurable dimension of the disease.

Non-target lesions. All other lesions (or sites of disease) including any measurable lesions over and above the 5 target lesions should be identified as **non-target lesions** and should also be recorded at baseline. Measurements of these lesions are not required, but the presence, absence, or in rare cases unequivocal progression of each should be noted throughout follow-up.

12.1.3 Methods for Evaluation of Measurable Disease

All measurements should be taken and recorded in metric notation using a ruler or calipers. All baseline evaluations should be performed as closely as possible to the beginning of treatment and never more than 4 weeks before the beginning of the treatment.

Version Date: 04-05-2021 v6.0

The same method of assessment and the same technique should be used to characterize each identified and reported lesion at baseline and during follow-up. Imaging-based evaluation is preferred to evaluation by clinical examination unless the lesion(s) being followed cannot be imaged but are assessable by clinical exam.

Clinical lesions Clinical lesions will only be considered measurable when they are superficial (e.g., skin nodules and palpable lymph nodes) and ≥ 10 mm diameter as assessed using calipers (e.g., skin nodules). In the case of skin lesions, documentation by color photography, including a ruler to estimate the size of the lesion, is recommended.

Chest x-ray Lesions on chest x-ray are acceptable as measurable lesions when they are clearly defined and surrounded by aerated lung. However, CT is preferable.

Conventional CT and MRI This guideline has defined measurability of lesions on CT scan based on the assumption that CT slice thickness is 5 mm or less. If CT scans have slice thickness greater than 5 mm, the minimum size for a measurable lesion should be twice the slice thickness. MRI is also acceptable in certain situations (*e.g.* for body scans).

Use of MRI remains a complex issue. MRI has excellent contrast, spatial, and temporal resolution; however, there are many image acquisition variables involved in MRI, which greatly impact image quality, lesion conspicuity, and measurement. Furthermore, the availability of MRI is variable globally. As with CT, if an MRI is performed, the technical specifications of the scanning sequences used should be optimized for the evaluation of the type and site of disease. Furthermore, as with CT, the modality used at follow-up should be the same as was used at baseline and the lesions should be measured/assessed on the same pulse sequence. It is beyond the scope of the RECIST guidelines to prescribe specific MRI pulse sequence parameters for all scanners, body parts, and diseases. Ideally, the same type of scanner should be used and the image acquisition protocol should be followed as closely as possible to prior scans. Body scans should be performed with breath-hold scanning techniques, if possible.

12.1.4 Response Criteria

12.1.4.1 Evaluation of Target Lesions

Complete Response (CR): Disappearance of all target lesions. Any pathological lymph nodes (whether target or non-target) must have reduction in short axis to <10 mm.

Partial Response (PR): At least a 30% decrease in the sum of the diameters of target lesions, taking as reference the baseline sum diameters.

Progressive Disease (PD): At least a 20% increase in the sum of the diameters of target lesions, taking as reference the smallest sum on study (this includes the baseline sum if that is the smallest on study). In addition to the relative increase of

Version Date: 04-05-2021 v6.0

20%, the sum must also demonstrate an absolute increase of at least 5 mm. (Note: the appearance of one or more new lesions is also considered progressions).

Stable Disease (SD): Neither sufficient shrinkage to qualify for PR nor sufficient increase to qualify for PD, taking as reference the smallest sum diameters while on study.

12.1.4.2 Evaluation of Non-Target Lesions

Complete Response (CR): Disappearance of all non-target lesions and normalization of tumor marker level. All lymph nodes must be non-pathological in size (<10 mm short axis).

Note: If tumor markers are initially above the upper normal limit, they must normalize for a patient to be considered in complete clinical response.

Non-CR/Non-PD: Persistence of one or more non-target lesion(s) and/or maintenance of tumor marker level above the normal limits.

Progressive Disease (PD): Appearance of one or more new lesions and/or *unequivocal progression* of existing non-target lesions. *Unequivocal progression* should not normally trump target lesion status. It must be representative of overall disease status change, not a single lesion increase.

Although a clear progression of "non-target" lesions only is exceptional, the opinion of the treating physician should prevail in such circumstances, and the progression status should be confirmed at a later time by the review panel (or Principal Investigator).

